### 4.3. Strategies for Recruitment and Retention

The study will enroll approximately 100 subjects across approximately 10 clinical sites in Europe. Once enrolled, each subject will participate in the study for up to 90 days post-procedure per the hospital's Standard of Care and the protocol schedule of assessments.

Principal investigators and clinical sites will be evaluated based upon the following factors:

- Previous experience with thrombectomy using large bore aspiration catheters: Each treating investigator must have performed at least 20 thrombectomy procedures using ADAPT, of which at least 2 cases are with the EMBOVAC™ device.
- Experience in conducting clinical studies.
- Currently treating subjects who meet the inclusion / exclusion criteria.
- Ability to enroll an adequate number of subjects.
- Ability to perform required clinical testing, including: angiography, CT, and/or MRI.
- Ability and willingness to provide the sponsor's representatives and local regulatory authorities access to the hospital records, study files, and subject files as they pertain to the study.
- Willingness to participate, including compliance with all aspects of the study.

Adequate staffing to conduct the study includes:

- Principal Investigator (PI): Responsible for overall clinical management of subjects enrolled at his/her institution. Assumes overall responsibility and accountability for the clinical team and for data obtained from each subject participating in the study. Ensures compliance with the protocol, applicable laws, and applicable regulations; ensures informed consents are signed, and reviews and signs electronic case report forms eCRFs indicating documents are accurate and complete.
- Sub-Investigator (Sub-I): Any individual member of the clinical trial team designated and supervised by the investigator to perform clinical trial-related procedures and/or make important trial-related decisions. A site is not required to have a Sub-I.
- Study Coordinator: Assists PI with study activities as delegated by the PI, including tracking subjects involved in the study, scheduling testing and follow-up visits, maintaining study records, completing eCRFs to the sponsor in a timely manner. A site is not required to have a Study Coordinator but must have an individual other than the PI dedicated to support the study.

To best capture real-world experience with the EMBOVAC™ Aspiration Catheter, the Sponsor will attempt to include a diversified group of investigational sites by engaging with a variety of institutions. To ensure generalizability of results, sites will be geographically distributed throughout Europe so that multiple countries are represented. Influence from any one site will be minimized by limiting maximum enrollment per site to 20 percent of overall study enrollment or approximately 20 subjects.

#### **4.4 Participant Withdrawal or Termination**

##### **4.4.1 Reasons for Withdrawal or Termination**

Subjects are free to withdraw from participation in the study at any time upon request. The investigator may terminate participation in the study if any adverse event or other medical condition or situation occurs such that continued participation would not be in the best interest of the participant.

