## 7.3. Procedure

The clinical decision to use the EMBOVAC™ Aspiration Catheter, as well as the revascularization procedure are independent (regardless) of the research. Physicians should follow the most current EMBOVAC™ Aspiration Catheter Instructions for Use (IFU) at all times with regards to the device compatibility, preparation and the recommended retrieval procedure. The research procedures are limited to the collection of data. Data will be collected before, during, and after use of the EMBOVAC™ Aspiration Catheter.

During the procedure, the following data will be collected:

- Total number of passes: A pass is defined as use of aspiration followed by evaluation of revascularization with angiography.
- Procedural angiography – The following will be recorded by the clinical site:
  - mTICI score per each attempted pass
  - Procedure Time defined as time from arterial puncture to complete recanalization (first mTICI  $\geq$  2b)
- Thrombectomy techniques and devices utilized per pass
- Additional interventions performed (if applicable)
- Record any reportable AEs per this protocol which occur during the procedure and up to the time of the 24hour examination.
- Clot collection per pass: this study aims to collect the clot from all subjects enrolled. However, in consideration of the urgent nature of stroke treatment, if the clot cannot be collected in a study procedure, it will not be considered a protocol deviation.

Once subject eligibility has been confirmed, the subject can be enrolled in the study.

**A subject is considered enrolled in this study once the physician confirms the subject meets all eligibility criteria and the subject or their legal representative has provided informed consent.**

A subject will not meet inclusion criteria and must not be enrolled if the EMBOVACTM Aspiration Catheter is not used for the first 3 clot removal passes for the target intracranial occlusion (unless use of another device is needed to remove clot in a distal vessel  $<2$ mm in diameter).

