## 7.8. Early Termination

During the study, it is possible that subjects will be withdrawn from the study. Factors leading to subject early termination may include, but are not limited to the following:

- Subject withdraws consent prior to study completion of all study follow up requirements
- The Investigator decides to discontinue subject's or site's participation in the study
- The subject is lost to follow-up
- Death
- The study is terminated at a site or as a whole

The study can be discontinued at the discretion of the investigator or study Sponsor for reasons including, but not limited to, the following:

- Obtaining new scientific knowledge that shows that the study is no longer valid or necessary
- Insufficient recruitment of subjects
- Persistent non-compliance of a site with the protocol, or EC regulatory requirements

If the study is discontinued or suspended prematurely at a single clinical site (e.g. due to non-compliance or lack of enrollment), the Sponsor shall inform the clinical investigator/investigational center of the termination or suspension in enrollment and the reason for this. The Sponsor will also inform site personnel that although enrollment will be halted, the currently enrolled subjects will continue to be followed per protocol through the 90-day follow-up visit and then be exited from the study. The Sponsor's communication to the investigator/investigational center will also include instructions for the investigator to promptly inform the EC regarding the change in study status, along with the reason for termination or suspension by the Sponsor.

If the entire study is discontinued or suspended prematurely, the Sponsor shall promptly inform all clinical investigators/investigational centers of the termination or suspension in enrollment and the reason for this.

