- **Modified Rankin Scale (mRS) 0-2 at 90 days**

The number and percentage of subjects achieving mRS 0-2 at 90 days (75 days or above) will be summarized with CIs. Subjects with missing mRS scores due to all-cause mortality are considered to have an mRS score of 6 in the analysis, subjects with missing mRS scores due to reasons other than all-cause mortality will be excluded. Subjects with mRS scores outside or didn't reach the 90-day window, due to reasons other than mortality, will be listed together with their mTICI scores at end of procedure.

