7.5.2.2 Secondary Safety Endpoints

Device-related SAEs and all-cause mortality, Kaplan-Meier analysis (using product limit estimates) will be applied. Kaplan-Meier event rate and its associated two-sided 95% CIs using log-log transformation will be reported, the estimate of standard error will be computed using Greenwood's formula.

- **Devices related serious adverse events (SAEs) within 90 days of follow up as determined by an independent Clinical Events Committee**

Kaplan-Meier analysis will be performed to analyze the device related SAE rate within 90 days. Device related SAEs are considered as events; where the event date is the date of first event. Subjects without events will be censored at the date of last contact. The event rate at 90 days with associated 95% CIs will be provided. Device related SAEs beyond 90 days will be listed.

- **sICH at 24h post procedure specified according to the Heidelberg Bleeding Classification (HBC) as determined by an independent Clinical Events Committee**

sICH at 24 hours post procedure as specified by HBC will be assessed. The number and percentage of subjects with events will be summarized with CIs.

- **NIHSS at 24h post procedure**

The observed NIHSS total score at 24 hours post-procedure and changes from the baseline score will be summarized.

- **90 Day All-Cause Mortality**

Kaplan-Meier analysis will be performed to analyze all-cause mortality within 90 days. All-cause mortality is considered as the event; where the event date is the date of mortality. Subjects without events will be censored at the date of last contact. The event rate at 90 days with associated 95% CIs will be provided. Deaths beyond the 90 days will be listed.

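### Nothing keeps 90-day follow-up going when the investigator ends participation for an adverse event, although participation is data collection only; this risks informative censoring in secondary outcomes

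*Protocol*

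**What the plan says.** Protocol 4.4.1 gives the investigator a discretionary power: "The investigator may terminate participation in the study if any adverse event or other medical condition or situation occurs", with the condition "such that continued participation would not be in the best interest of the participant". Protocol 7.8 includes among the causes of early termination "The Investigator decides to discontinue subject's or site's participation in the study", without naming an adverse event as the ground.

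Protocol 7.3 describes what participation involves: "The research procedures are limited to the collection of data". Section 6 says the same, and 7.6 allows the 90-day AE review and mRS to be done by telephone.

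Protocol 4.4.2 has termination in its title, but its rules on follow-up and on excluding later data are written for subjects who withdraw. It has no separate rule for a subject whose participation the investigator ends.

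SAP 7.5.2.2 analyses 90-day mortality and device-related SAEs by Kaplan-Meier: "Subjects without events will be censored at the date of last contact". For mRS 0-2, SAP 7.5.2.1 scores deaths as 6 and says "subjects with missing mRS scores due to reasons other than all-cause mortality will be excluded".

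Protocol 7.8 also lists "The study is terminated at a site or as a whole" as a cause of subject early termination. Further down, for a site that is stopped, it says that "currently enrolled subjects will continue to be followed per protocol through the 90-day follow-up visit".

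**The concern.** In a trial with continuing treatment, a best-interest clause lets the investigator take a subject off that treatment. Here there is none to take the subject off. Ending participation can only end observation, and the stated trigger is an adverse event or a medical condition.

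Kaplan-Meier estimation assumes that subjects censored at a given time have the same later risk as those still followed. Censoring prompted by an adverse event is likely to break that assumption. A complete-case mRS rate has the same weakness if those dropped would mostly have scored above 2. At stake are the 90-day mortality, device-related SAE and mRS 0-2 results, which are the study's clinical outcome evidence on the device.

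**Working it through.** **The plan's own figure.** Both documents give a margin of error of 8.0% for the primary endpoint. 1.96 × √(0.8 × 0.2 / 95) = 0.0804, so it is reproduced. It concerns an outcome read at the end of the procedure, which later termination cannot change. The plan gives no expected mortality, mRS or termination rate, so everything below rests on assumed counts.

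**What is lost and what is kept.**
- Protocol 4.4.2 keeps data collected before a withdrawal, so an SAE that prompts termination is counted. The SAE analysis uses the first event, so the only loss is a first device-related SAE that occurs after termination.
- A death known to the study counts in the mortality analysis and scores mRS 6. Only deaths after contact ends are missed.
- A missing 90-day mRS in a subject not known to have died leaves the denominator.

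**Mortality.** Assume N = 100, D true deaths by day 90, k subjects terminated, and h of those k dying unseen. The Kaplan-Meier estimate lies between two bounds:
- censoring before all other deaths: (D − h)/(100 − k)
- censoring after all other deaths: (D − h)/100

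With D = 15, k = 3, h = 3: 12/97 = 12.4% and 12/100 = 12.0%, against 15.0%.

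With D = 15 and k = 5 (h may be an expected, non-integer count):

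| Share of the five dying unseen | h | Early censoring | Late censoring |
|---|---|---|---|
| all | 5 | 10/95 = 10.5% | 10.0% |
| half | 2.5 | 12.5/95 = 13.2% | 12.5% |
| one in five | 1 | 14/95 = 14.7% | 14.0% |
| none | 0 | 15/95 = 15.8% | 15.0% |

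If three subjects are censored early and then die at the overall 15% rate, h = 3 × 0.15 = 0.45 and the estimate is 14.55/97 = 15.0%: no bias.

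**mRS 0-2.** Assume that all k would have scored above 2 and that none is known to have died. The observed rate is then (true successes)/(100 − k).
- True 45%: 45/97 = 46.4% for k = 3; 45/95 = 47.4% for k = 5.
- True 55%: 55/97 = 56.7% for k = 3; 55/95 = 57.9% for k = 5.

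**Scale.** By the normal approximation, the 95% half-width for 15% mortality in 100 subjects is 1.96 × √(0.15 × 0.85 / 100) = 7.0 points. The three-death example shifts the estimate by 2.6 to 3.0 points.

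**Section 7.8 against itself.** The list makes termination at a site a reason for a subject to leave early, while the later paragraph has subjects at a stopped site followed to day 90. For termination of the whole study, the section requires that investigators be informed but does not mention follow-up.

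**The case against.** The power is permissive and conditional. Because participation is only data collection, the best-interest condition should seldom be met. A reader might infer that follow-up does end in the sickest subjects and that the 90-day results are therefore biased favourably. The documents do not support that: they do not show that the rule will be used, and they do not expressly say that data collection stops when it is. A reader might also take 7.8 to name an adverse event as a ground. It does not.

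The plan also makes affected subjects visible. SAP 7.2 reports early terminations with reasons. SAP 7.5.2.1 lists subjects without an in-window mRS alongside their final mTICI. SAP 7.11 carries forward the last post-procedure mRS. The endpoints concerned are secondary and descriptive, and SAP section 4 says the intervals are not for inference. The 5% attrition figure supports the precision of the primary endpoint, so it is not a limit on 90-day terminations.

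All of this stands, and it makes the point a risk of unstated size. It does not close the gap. Carrying a score forward needs a post-procedure mRS, which Protocol 7.5 makes optional at discharge, and mortality and SAEs have no sensitivity analysis. A disposition table shows why subjects left but does not recover their outcomes. The wording of 7.8, which speaks of subjects being withdrawn, leaves it open to a site to apply the exclusion in 4.4.2 to investigator terminations.

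The list in 7.8 is non-exhaustive and the later paragraph reads as the operative rule, so that inconsistency is small.

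**Conclusion.** The point holds as a gap in follow-up. The protocol allows participation to end on a trigger related to prognosis, in a study where ending it stops nothing but observation, and it does not preserve outcome collection afterwards. If the power is used, secondary 90-day mortality, later first device-related SAEs and mRS 0-2 are exposed to informative censoring or selective exclusion.

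The probable direction is favourable, on the assumption that terminated subjects fare worse than those who stay. Under the assumed counts with k up to 5, the worst cases are about 5 points too low for mortality, only if all five die unseen, and 2.4 to 2.9 points too high for mRS 0-2. If terminated subjects have no higher later mortality than comparable subjects still followed, there is no favourable mortality bias.

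**What to change.** In Protocol 4.4.2 and 7.8, state that an investigator's decision to end participation does not end collection of vital status, reportable AEs and the 90-day mRS (by telephone if needed) while consent stands, and that only withdrawal of consent does. The best-interest clause in 4.4.1 can remain.

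In 7.8, reconcile the listing of site termination as a cause of subject early termination with the paragraph that follows such subjects through day 90.

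The cost is a few extra telephone contacts and a wording amendment, which under Protocol 11.2 needs ethics committee approval before it takes effect.

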##### **4.4.2 Handling of Participant Withdrawals or Termination**

Subjects that withdraw consent after treatment are not required to undergo follow-up after withdrawal. They will not be replaced and will be considered part of the subject cohort. The reason for early withdrawal will be documented in the source documents and case report forms.

In the event a subject withdraws from the study, their data will be excluded from the data analysis from the time of withdrawal going forward and any remaining clot sample from that subject will be discarded by the Clot analysis lab if no longer needed for study purposes (i.e., will not be stored for future research purposes). All data collected prior to withdrawal will be included in for data analysis, as permitted per country regulations.

### **5. Study Device**

[figure not shown]
#### **5.1 Study Device Description**

##### **5.1.1 Device Acquisition**

The EMBOVAC™ Aspiration Catheter is CE Marked. As a result, shipments will not be tracked for this study, devices will be fully traceable though the company's 21 CFR 820 and ISO 13485 compliant quality system.

### 5.1.2 Device Returns

Any suspected device malfunction with the EMBOVAC™ Aspiration Catheter should be properly documented on the Electronic Case Report Forms (eCRFs). In the event of a suspected malfunction, the device should be returned to Cerenovus for analysis. Site will retain tracking information. All study devices should be returned to:

## 6. Study Procedures and Evaluations

The medical devices used and all treatment related activities (i.e. the tests and procedures) carried out during this study are in line with Good Clinical Practice and are conducted per standard operating policies at the treating hospital (study site). The conduct of this study does not affect the hospitals standard operating policies and does not impact the patient's standard of care.

Study-related activities exclusively consists of the structured collection and evaluation of data; this includes the patient angiographic imaging and analysis of blood clots retrieved from the patient during the procedure. This data (as outlined in the informed consent form) will only be shared with the Sponsor if a signed informed consent is obtained from the study subject or their legal authorized representative.

### 6.1. Study Specific Procedures

The procedures completed as part of this study are in line with SOC and include relevant medical history, relevant medication history, NIHSS, mRS, imaging (CT/MRI), procedural angiography and review of any reportable AEs. Patients presenting with acute ischemic stroke should be evaluated by the physician, in accordance with their institutional practice, to establish an appropriate treatment plan based on the subject's medical condition and available diagnostic screening procedures prior to enrollment in the study.

Clot samples will be collected on a per pass basis and shipped by the site to the Clot analysis lab for follow on analysis.

#### 6.1.1. Imaging

In this study, revascularization will be measured by an independent adjudicating Imaging Core Lab and reported using the eTICI (inclusive of the 2C rating) scale [19]. For purposes of data comparisons, a minimum threshold of mTICI 2b is equal to eTICI 2b50.

**Table 3 eTICI Scale**

0	No reperfusion; 0% filling of the downstream territory,
1	Thrombus reduction without any reperfusion of distal arteries
2	
 
• 2a Reperfusion in less than half (1-49%) of the territory
 
• 2b50 Reperfusion in (50-66%) of downstream territory
 
• 2b67 Reperfusion in (67-89%) of downstream territory
 
• 2c Reperfusion in (90-99%) of downstream territory
 

3	Complete or 100% reperfusion

All imaging should be in line with SOC. This includes CT or MR at baseline and 24 hours post procedure to assess any presence of hemorrhage, recanalization of the occluded artery, reperfusion, and infarct growth. Angiographic images obtained during the study should consist of (1) Baseline angiogram - prior to device advancement to assess clot location, (2) Post device angiogram - after each reperfusion attempt/pass of the device (a pass being defined as use of aspiration followed by evaluation of revascularization with angiography), (3) Final Angiogram – after all treatment has been completed. Any other imaging of the head or neck performed per SOC (for example as a result of clinical deterioration) must also be provided.

#### **6.1.2. Independent Imaging Core Lab for Image Evaluation**

All imaging collected will be SOC, no additional imaging will be requested for this study. An independent Imaging Core Lab will be utilized to provide an unbiased and standardized assessment of all collected imaging. All subject PHI will be removed before an image is uploaded and evaluated by the Imaging Core Lab.

The objective of the Imaging Core Lab will be to:

- Review all angiograms obtained
- Provide an unbiased assessment of the rate of revascularization defined by mTICI score based on angiographic imaging from the study sites
- Evaluate CT/MRI examinations to detect and assess hemorrhages.

This study will be collecting the following imaging data to be assessed by Imaging Core Lab:

**Baseline - CT/ MR imaging**

- ASPECTS (Alberta Stroke program early CT score)
- Infarct volume
- Clot location
- Clot length
- Clot density
- Clot enhancement

**Procedural Angiography**

- eTICI score for every pass
- Emboli to new territories
- Collateral score

**Post Procedure - CT/ MR imaging**

- Infarct volume
- Intracranial Hemorrhage

Hemorrhages will be classified according to the following categories [18]:

- HI 1 – Scattered small petechiae, no mass effect
- HI 2 – Confluent petechiae, no mass effect
- PH1 – Hematoma within infarcted tissue, occupying <30%, no substantive mass effect
- PH2 – Hematoma occupying 30% or more of the infarcted tissue, with obvious mass effect
- RIH – Parenchymal hematoma remote from infarcted brain tissue
- IVH – Intraventricular Hemorrhage
- SAH – Subarachnoid Hemorrhage
- SDH – Sub Dural Hemorrhage

The Imaging Core Lab assessor will be blinded to subjects' chart/clinical records. Each angiogram will be read independently by an experienced Imaging Core Lab Neurology reviewer.

### **6.1.3. Procedural Angiogram Shipment**

A copy of the angiograms collected during the study will be submitted to the independent Imaging Core Lab electronically via batch upload through the Imaging Core Lab website or through shipping pseudonymized imaging discs. All personally identifying information (e.g., name, date of birth, etc.) will be removed from images.

